### **7.1 Inclusion Criteria**

Patients must meet the following criteria to be enrolled in this study:

1. The patient's legal guardian(s) must provide written informed consent prior to study assessments being performed;
2. The patient must have a confirmed diagnosis of Pompe disease as determined by deficient endogenous GAA activity or GAA mutation analysis; and
3. The patient must be <1 year of age at time of study enrollment (and receive alglucosidase alfa treatment before 1 year of age), or the patient must be between 1 year and 24 months of age and must have initiated alglucosidase alfa treatment prior to turning 1 year of age.

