# **9. EFFICACY, SAFETY, AND EXPLORATORY VARIABLES**

## **9.1 Schedule of Assessments**

The study will be conducted in conjunction with the patient's standard of care as outlined in the following sections. [Table 9-1](#) summarizes the Schedule of Assessments at each visit period for patients enrolled into this study. With the exception of the Baseline, Day 0 and biweekly study assessments, all other assessments have a window of +/- 60 days. Any assessments conducted as standard of care 30 days before start of first study infusion may be utilized for baseline assessment provided all required information is captured. Infusions received after signing of the informed consent form and before completion of baseline assessments will be captured as a Concomitant Medication on CRF. Details of the assessments are provided in the SM.

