## **9.5 Adverse Events**

AEs will be assessed at screening/baseline. At every infusion visit the patient's legal guardian(s) will be asked "Since your last questioning or visit, has the patient experienced any health problems?"

An AE is defined as any undesirable physical, psychological or behavioral effect experienced by a patient or subject during their participation in an investigational study, in conjunction with the use of the drug or biologic, whether or not product-related. This includes any untoward signs or symptoms experienced by the patient from the time of signing of the informed consent until completion of the study.

AEs may include, but are not limited to:

- Subjective or objective symptoms spontaneously offered by the patient or subject and/or observed by the Investigator or medical staff
- Findings at physical examinations
- Laboratory abnormalities of clinical significance

Disease signs, symptoms, and/or laboratory abnormalities already existing prior to the use of the product (i.e., prior to participation in the AGLU03606 study) are not considered AEs after treatment unless they recur after the patient has recovered from the preexisting condition or in the opinion of the Investigator they represent a clinically significant exacerbation in intensity or frequency.

Any signs and symptoms experienced by the patient from the time of signing of the informed consent through the final study visit will be recorded on the CRF.

If clinically significant worsening from Baseline is noted, the changes will be documented as AEs on the AE CRF. Clinical significance is defined as any variation in signs, symptoms, or testing that has medical relevance and may result in an alteration in medical care. The Investigator will continue to monitor the patient until the parameter returns to Baseline or until the Investigator determines that follow-up is no longer medically necessary.

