4 STATISTICAL ANALYSES

4.1 GENERAL CONSIDERATIONS

In general, continuous data will be summarized using the number of observations available, mean, standard deviation (SD), median, minimum, and maximum. Categorical and ordinal data will be summarized using the counts and percentages of patients.

The baseline value is defined as the value measured at the Screening/Baseline visit prior to the first infusion during this study. In cases where a patient has more than one value measured during Screening/Baseline, the latest value will be the one used as baseline.

Unless otherwise specified, analyses will be performed for Full Analysis Set (FAS).

Observation period

The observation period will be divided into 2 segments:

- The **pre-treatment period** is defined as the period up to first IMP administration (ie, when the patients started receiving the alglucosidase alfa in the study, even if the patient had received alglucosidase alfa prior to entering the study).
- The **on-treatment period** (ie, treatment-emergent (TE) period) is defined as the period from the first IMP administration in the study to the last study assessment.

The on-study period is defined as the time from the signing of the informed consent until the end of the study (defined as the completion date or the discontinuation date collected on the case report form (CRF) page “Completion/Discontinuation”).

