4.7.2 Adverse events

General common rules for adverse events

All adverse events (AEs) will be coded to a lower-level term (LLT), preferred term (PT), high-level term (HLT), high-level group term (HLGT), and associated primary system organ class (SOC) using the Medical Dictionary for Regulatory Activities (MedDRA) version in effect at Sanofi at the time of database lock.

The AEs will be analyzed in the following 2 categories:

- Pre-treatment AEs: AEs that developed, worsened, or became serious during the pre-treatment period.
- Treatment-emergent adverse events (TEAE)s: AEs that developed, worsened, or became serious during the treatment-emergent period

Deaths during the study period will be provided in a listing.

The primary focus of AE reporting will be on TEAEs. Pre-treatment AEs will be described separately.

An AE with incomplete or missing date/time of onset (occurrence, worsening, or becoming serious) will be classified as a TEAE unless there is definitive information to categorize it as a pre-treatment or a post-treatment AE.

If the assessment of the relationship to IMP is missing for an AE, this AE will be assumed as related to IMP. If the severity is missing for 1 of the treatment-emergent occurrences of an AE, the severity will be imputed with the maximal severity of the other occurrences. If the severity is missing for all the occurrences, the severity will be left as missing.

Multiple occurrences of the same event in the same patient will be counted only once in the tables within a treatment phase.

The AE tables will be sorted as indicated in [Table 4](#).

Table 4 - Sorting of AE tables

AE presentation	Sorting rules
SOC and PT	By the internationally agreed SOC order and decreasing frequency of PTs ^{a, b}

a Sorting will be based on the overall number of patients.

b The table of all TEAEs presented by SOC and PT will define the presentation order for all other tables (eg, treatment-emergent SAE) presented by SOC and PT, unless otherwise specified.

Analysis of all adverse events

The overview of TEAE with event count and number (%) of patients will be generated:

- Any AE
- Any TEAE
 - TEAE related to the study drug
 - TEAE unrelated to the study drug
- TEAEs by severity (mild, moderate, severe)
- TEAEs by gender
- Any treatment emergent SAE
- Any treatment emergent SAE considered related to study drug
- Any protocol-defined infusion-associated reactions
- Any TEAE leading to treatment adjusted

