AEs for potential anaphylactic reactions, immune mediated reactions, and hypersensitivity reactions will be identified by respective standardized MedDRA queries (SMQ) (see [Table 6](#)). The results of the searches will be presented in listings. The most recent version of each MedDRA SMQ at the time of analysis will be used.

Table 6 - Selections for IARs and other TEAEs of interest

IARs and other TEAEs of interest	Selection
Protocol-defined IARs	e-CRF specific tick box on the AE page
Algorithm-defined potential IARs	all AEs occurring during an infusion or within 2 hours after the completion of an infusion; and all AEs occurring from >2 to 24 hours after the completion of an infusion
Potential anaphylactic reactions	MedDRA SMQ ^b of anaphylactic reactions
Potential immune mediated reactions	MedDRA SMQs ^b of Vasculitis and Severe cutaneous adverse reactions plus the Preferred Terms of glomerulonephritis, nephrotic syndrome, proteinuria, hematuria, vasculitis, serositis, myocarditis, skin lesion, skin necrosis, arthralgia, arthritis, myalgia, arthropathy, lymphadenopathy, serum sickness, type III immune complex mediated reaction, and influenza like illness ^a
Potential hypersensitivity reactions	MedDRA SMQ ^b of hypersensitivity

^a The list of terms may be adjusted according to MedDRA version changes.

^b The most recent version of each MedDRA SMQ at the time of analysis will be used.

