5.4.3 Analysis windows for time points

The following analysis windows will decide how the scheduled and/or unscheduled visits will be used in the by-visit analyses of efficacy, safety, and exploratory variables.

A measurement (scheduled or unscheduled) will be used if it is available and measurement date is within the analysis window.

After applying these time windows, if multiple assessments are associated to the same time point, the closest from the targeted study day will be used. Except where specified otherwise, if the difference is a tie, the value after the targeted study day will be used. If multiple valid values exist within a same day, then all the valid values of the day will first be averaged before applying the

aforementioned rules. (Note that the rule of using the later date of the window does not conflict with any protocol-specified procedure that has to be done pre-infusion (eg, IgG assessments), as all IgG assessments will be performed prior to infusion unless there was a protocol deviation.)

If there is no measurement for a given parameter in an analysis window, data will be considered missing for the corresponding visit.

Efficacy assessments

The schedule for the efficacy assessments is shown in the following table.

Efficacy assessments	Schedule
Recumbent length/height, weight, and head circumference	Every 3 months age < 3 years; every 6 months 3 to <5 years, every 12 months \geq 5 years
Bayley-III	every 6 months ages 1 month to 42 months
Leiter-R/Leiter-3	from final Bayley-III assessment < 42 months of age, every 12 months
GMFM-88	every 6 months age < 5 years; every 12 months \geq 5 years
Pompe PEDI	every 6 months age < 5 years; every 12 months \geq 5 years

Given that patients enter study at different ages, if we define analysis windows for the efficacy endpoints based on the assessment schedule, the definitions will vary depending on each patient's age at study entry. In addition, due to the small patient population, we will focus on individual patient growth by age. The following analysis windows for efficacy assessments will not be used in by-visit summary tables or figures, but may be used in the patient listing to associate observations to the nearest study visits.

Maximum age at signing of the informed consent was 1.9 years.

Table 7 - Analysis window definition for recumbent length/height, weight, and head circumference

Scheduled visit post baseline	Targeted study day	Analysis window in study day

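### Adverse events that arise on alglucosidase alfa between consent and the first study infusion are classed as pre-treatment and left out of the TEAE summaries; their place in the IAR counts is unclear

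*SAP*

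**What the plan says.** **Who enters.** Protocol 7.1 admits infants under 1 year. It also admits children aged 1 year to 24 months, who "must have initiated alglucosidase alfa treatment prior to turning 1 year of age". SAP 5.4.3 records that "Maximum age at signing of the informed consent was 1.9 years".

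**What happens after consent.** Protocol 9.1: "Infusions received after signing of the informed consent form and before completion of baseline assessments will be captured as a Concomitant Medication on CRF". No maximum interval from consent to first study infusion is given. Protocol 9.5 starts AE collection at consent.

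**How time is divided.** SAP 4.1 ends the pre-treatment period at the first administration of study drug, "even if the patient had received alglucosidase alfa prior to entering the study". The on-treatment period "is defined as the period from the first IMP administration in the study to the last study assessment".

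**How AEs are sorted.** SAP 4.7.2 has two classes. One reads "Pre-treatment AEs: AEs that developed, worsened, or became serious during the pre-treatment period"; the other is the TEAE, defined in the same way for the on-treatment period. Reporting concentrates on TEAEs.

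**How IARs are selected.** Table 6 of the SAP appears under the heading "IARs and other TEAEs of interest". Its rule for protocol-defined IARs is a tick box on the AE page. Its rule for algorithm-defined potential IARs takes every AE during an infusion or in the 24 hours after its completion.

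**The concern.** A child already on treatment has no drug-free run-in and no wash-out before the first study infusion. For that child, pre-treatment does not describe the time between consent and Day 0: the drug is being given, AEs are being collected, and only the label on the infusion differs.

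The sentence in Protocol 9.1 is not restricted to already-treated children. If a child untreated at consent is infused before baseline is complete, the first exposures of that child's life also fall in the gap.

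The secondary objective is long-term safety in these patients, and Protocol section 11 promises summaries of AEs, SAEs and IARs without a treatment-emergent restriction. Under the SAP, a drug-related or serious event in the gap would reach none of the summaries that show relatedness or seriousness. For IARs, two programmers following the SAP could produce different counts.

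**Working it through.** There is no sample size, power or event figure in the plan to reproduce. The check sets the definitions against each other and then sizes the gap.

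**Step 1. Can an AE occur on drug in the pre-treatment period?**
- Already-treated children are eligible (Protocol 7.1). The maximum age at consent is 1.9 × 12 = 22.8 months, so at least one of the 12 enrolled (SAP 5.2) was already on treatment, provided that patient met the inclusion criteria.
- Infusions between consent and completion of baseline are foreseen and are not recorded as study infusions (Protocol 9.1).
- AEs are recorded from consent (Protocol 9.5).
- The pre-treatment period runs to the first study infusion (SAP 4.1).

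The answer is yes. The wording of SAP 4.1 alone would not show this; it needs Protocol 9.1 for the dosing after consent.

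**Step 2. Where does such an AE appear (SAP 4.7.2)?**

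| Output | AE confined to the gap |
|---|---|
| Any AE row of the overview | included |
| Pre-treatment AE table by SOC and PT | included |
| Individual listings promised in Protocol 11 | included |
| Listing of deaths during the study | included if fatal |
| All TEAEs; related TEAEs; TEAEs by maximal severity | not included |
| Treatment-emergent SAEs, all and related | not included |
| TEAEs leading to discontinuation or to death | not included |
| Protocol-defined and algorithm-defined IARs | not determined |

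If the event worsens or becomes serious after the first study infusion, it becomes a TEAE. An event with an unclear onset date defaults to TEAE. The exclusion therefore applies to events that both start and stay in the gap.

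**Step 3. Why IARs are not determined.** Neither selection rule names a period or restricts the infusion to study-labelled drug, so read literally both take gap reactions. Against that, the Table 6 heading describes the listed items as TEAEs, and the IAR row stands in an overview of TEAEs.

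**Step 4. Size.** The gap length is an assumption; 30 days is borrowed from the baseline look-back in Protocol 9.1. On an unbroken 14-day cycle, infusions in the gap = floor(gap / 14), since the gap ends on an infusion day. Share of observed days = gap / (gap + follow-up), for follow-up of 365, 1,460 and 3,650 days.

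| Gap (days) | Infusions per already-treated patient | Ceiling if all 12 were already treated | Share, 1 year | Share, 4 years | Share, 10 years |
|---|---|---|---|---|---|
| 14 | 1 | 12 | 3.69% | 0.95% | 0.38% |
| 30 | 2 | 24 | 7.59% | 2.01% | 0.82% |
| 60 | 4 | 48 | 14.12% | 3.95% | 1.62% |
| 90 | 6 | 72 | 19.78% | 5.81% | 2.41% |

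For the 30-day row: floor(30 / 14) = 2; 30 / 395 = 7.59%; 30 / 1,490 = 2.01%; 30 / 3,680 = 0.82%. Ten years of fortnightly dosing is 3,650 / 14 + 1, or about 261 infusions. The shorter follow-ups matter because SAP 5.2 reports that 7 of the 12 withdrew or died in less than 4 years.

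If all 12 are analysed, one patient whose only event of a given type falls in the gap changes its incidence by 1 / 12 = 8.3 percentage points.

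**The case against.** The rule is explicit and consistent. SAP 4.1 considered earlier treatment and chose the first study infusion as its anchor. Baseline, study-drug exposure, compliance, antibody timing, prior medication and Day 0 use the same anchor. With 12 patients, listings show each case. All of this stands. It answers a charge of concealment, but it does not supply relatedness or seriousness summaries for gap events.

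It could also be said that an infusion after consent is already one given in the study. Protocol 9.1 points the other way: it records these infusions as concomitant medication and speaks separately of the first study infusion. The SAP does not address the point.

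Four stronger readings are tempting, and the documents do not support them:
- *That gap infusion reactions are excluded from the IAR counts.* No exclusion is stated; a heading and the placement of a row suggest one.
- *That gap AEs are lost.* They are kept apart in their own table and remain in the Any AE row.
- *That the oldest entrant's treatment before consent, more than 1.9 − 1.0 = 0.9 year, measures the misclassification.* That time precedes AE collection in this study.
- *That many events are affected.* No document shows that any patient had an infusion or an AE in the gap.

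There is also a sound objection to moving the start of the whole on-treatment period. That period drives the PCSA and abnormal-ECG incidences and the concomitant-medication classification. Starting it at consent would bring baseline assessments into the on-treatment data.

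**Conclusion.** The misclassification is real and follows from the documents' own definitions: AEs on alglucosidase alfa after consent and before the first study infusion are labelled pre-treatment and kept out of every treatment-emergent summary. For IARs the plan is ambiguous and should be settled before analysis.

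The number of patients and events affected is not stated. At least one already-treated patient enrolled, if eligible. Under an assumed 30-day gap and unbroken fortnightly dosing, about 2 infusions per such patient are involved: a small share of long follow-up, and a larger one for patients lost early. This is a contained defect in the safety summaries. It does not put the safety data as a whole in doubt.

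**What to change.** Confine the change to AE and IAR classification. Leave the baseline, Day 0, exposure, PCSA, ECG and antibody anchors as they are.

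1. In SAP 4.7.2, define on-drug AEs as those with onset on or after the first alglucosidase alfa infusion following consent, counting infusions recorded as concomitant medication. For patients already on treatment at consent, start at consent.
2. Report them either within the TEAE tables or in a separate row for AEs on alglucosidase alfa before the first study infusion, showing relatedness and seriousness.
3. State in Table 6 that both IAR definitions include reactions to these infusions.
4. As a side point, align Protocol 9.5, which treats the time "prior to the use of the product (i.e., prior to participation in the AGLU03606 study" as one and the same; for already-treated patients it is not.

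The cost is SAP wording and one extra derivation date. AE and IAR counts may rise slightly, and some counted AEs will fall outside the study-drug exposure period, which a table footnote should say.

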4.2 PATIENT DISPOSITIONS

The number (%) of patients included in the analysis population listed in [Table 3](#) will be summarized.

The number (%) of patients in the following categories will be provided:

- Screened patients
- Enrolled patients
- Enrolled and treated patients
- Patients who completed the study period as per protocol
- Patients who did not complete the study period as per protocol and main reason for study discontinuation
- Patient status at last study contact (alive, deceased)

A listing will be provided with completion/discontinuation dates, study duration (days), and all discontinuation reasons.

Protocol deviations

Critical and major protocol deviations (automatic or manual) will be summarized in the enrolled population.

4.3 PRIMARY ENDPOINT(S) ANALYSIS

4.3.1 Definition of endpoint(s)

Physical growth

The endpoints for physical growth are defined as changes from baseline to study time points in recumbent height/length, weight, and head circumference. Changes in Z-scores (standardized age and gender adjusted values) for height/length, weight, and head circumference based on Center for Disease Control (CDC) Growth Charts will also be calculated. Refer to protocol Section 9.2.1 for the details of measurement. Also refer to [Section 5.2](#) for the rationale to incorporate World Health Organization (WHO) growth charts for children <24 months of age.

Motor development

Motor development and function is measured by changes in the motor subscale of the Bayley Scales of Infant and Toddler Development (Bayley-III) (up to 42 months of age), Gross Motor Function Measure (GMFM-88), and Pompe Pediatric Evaluation of Disability Inventory (Pompe PEDI). Change from baseline to study time points will be calculated for the following parameters:

- Bayley-III: raw scores, scaled scores, and composite scores reported for each of the 3 administered scales (cognitive, language, and motor) for patients from 1 month to 42 months of age.
 - The Language scale includes the Receptive and Expressive subtests
 - The Motor scale includes the Fine Motor and Gross Motor subtests
- GMFM-88: total raw score, total score (average of dimension percentage scores) and dimension scores of 5 dimensions (lying and rolling; sitting; crawling and kneeling; standing; walking, running, and jumping). GMFM-88 summary score will be calculated as described in protocol Section 9.2.2.3.
- Pompe PEDI: scores (raw, scaled, normative standard) by scale (functional skills, caregiver assistance) and domain (self-care, mobility, social function)

Refer to protocol Section 9.2.2 for the definitions and measurement details of Bayley-III, GMFM-88 and Pompe PEDI.

Cognitive function

Cognitive function is measured by the cognitive and language subscales of the Bayley Scales of Infant and Toddler Development (Bayley-III) (up to 42 months of age), change in the Brief IQ score of the Leiter International Performance Scale - Revised (Leiter-R) and/or the change in the Nonverbal IQ score of the Leiter International Performance Scale - 3rd Edition (Leiter-3) (starting at the final assessment of the Bayley-III before 42 months of age). Change from baseline to study timepoints in the raw and scaled scores for the 4 subtests will be calculated. Refer to protocol Section 9.2.2 for the definitions and measurement details of Bayley-III, Leiter-R, and Leiter-3.

During the study, the Leiter-R was replaced with the updated Leiter-3. Patients that had previously been evaluated with the Leiter-R had a concurrent assessment with the Leiter-3 before transitioning to the Leiter-3 throughout the study in order to monitor impact of tool differences on change in scores. For these patients, multiple Leiter assessments at the transition study visit will be reported.

Pompe PEDI, Bayley-III, Leiter-R, and Leiter-3 will be centrally scored by an external consultant.

All efficacy assessments collected during the study will be used, including any obtained after IMP discontinuation.

